8.3 EVENTS AND SERIOUS ADVERSE EVENTS

8.3.1 DEFINITION OF EVENTS

As this is not a treatment study, the typical definition of adverse events does not apply, as there is no treatment intervention with which adverse events could be associated.

However, untoward medical occurrences (events) may be identified during the course of the study.

Events that are not related to study procedures and that do not meet criteria for serious adverse events as described below will not be recorded. Events related to study procedures will be recorded.

8.3.2 DEFINITION OF SERIOUS ADVERSE EVENTS (SAE)

An adverse event (AE) or event is considered "serious" if, in the view of either the investigator or sponsor, it results in any of the following outcomes:

The following events are considered **Serious adverse events (SAE)**

- death
- a life-threatening adverse event (Stroke, MI, fracture, suicide attempt)
- inpatient hospitalization
- prolongation of existing hospitalization
- a persistent or significant incapacity (last more than 48 hours and limits activities of daily living)
- a congenital anomaly/birth defect

Important medical events that may not result in death, be life-threatening, or require hospitalization may be considered serious when, based upon appropriate medical judgment, they may jeopardize the participant and may require medical or surgical intervention to prevent one of the outcomes listed in this definition.

8.3.3 CLASSIFICATION OF AN EVENT OR SERIOUS ADVERSE EVENT

8.3.3.1 SEVERITY OF EVENT

For events related to the study procedures, the following guidelines may be used to describe severity.

- **Mild** – Events require minimal or no treatment and do not interfere with the participant's daily activities.
- **Moderate** – Events result in a low level of inconvenience or concern with the therapeutic measures. Moderate events may cause some interference with functioning.
- **Severe** – Events interrupt a participant's usual daily activity and may require systemic drug therapy or other treatment. Severe events are usually potentially life-threatening or incapacitating. Of note, the term "severe" does not necessarily equate to "serious".

8.3.3.2 RELATIONSHIP TO STUDY PARTICIPATION

All serious adverse events (SAEs) must have their relationship to study participation assessed by the clinician who examines and evaluates the participant based on temporal relationship and his/her clinical judgment.

The degree of certainty about causality will be graded using the categories below.

- **Possibly related** – A “possibly related” serious adverse event reflects a realistic chance of a causal relationship between a study procedure and the adverse event. Reasonable possibility means that there is evidence to suggest a causal relationship between the study procedure as suggested by an event that follows within a reasonable time after the study procedure (i.e., 24 hours), follows a pattern consistent with the study procedure.
- **Not Related** – There is not a reasonable possibility that the administration of the study procedure caused the serious adverse event, there is no temporal relationship between the study procedure and event onset, or an alternate etiology has been established.

8.3.3.3 EXPECTEDNESS

The Principal Investigator will be responsible for determining whether a serious adverse event (SAE) or a study related event is expected or unexpected.

- Expected: Any event that is listed in protocol, consent form, or part of the normal disease condition.
- Unexpected: Any event that is not listed in the protocol, consent form, or is not part of the normal disease progression.

8.3.4 TIME PERIOD AND FREQUENCY FOR EVENT ASSESSMENT AND FOLLOW-UP

The occurrence of an event or serious adverse event (SAE) may come to the attention of study personnel during outcome assessments or at other contacts between study staff and participants. Serious adverse events (SAE) may come to the attention of study personnel during medical record review for health utilization outcome assessment.

All study-procedure related events not meeting the criteria for SAEs will be captured on the appropriate case report form (CRF). Given the minimal risk of the study procedures, these events are expected to be rare.

Any SAEs will also be captured on the appropriate case report form.

Information to be collected includes:

- event description,
- time of onset and duration
- clinician’s assessment of severity,
- time of resolution/stabilization of the event.

All study related events will be followed to adequate resolution.

Any medical condition that is present at the time that the participant is screened will be considered as baseline and not reported as an event. However, if the study participant's condition deteriorates at any time during the study and then meets the definition of an SAE, it will be recorded as an SAE.

Changes in the severity of an event or SAE will be documented to allow an assessment of the duration of the event at each level of severity to be performed.

The Study team will record all reportable events with start dates occurring any time after informed consent is obtained until 7 (for non-serious study related events) or 30 days (for SAEs) after the last day of study participation. Events will be followed for outcome information until resolution or stabilization.

8.3.5 EVENT REPORTING

All study related events will be reviewed by the PI and will be reported to the IRB if the events meet criteria for IRB reporting via IRB policy, or at a timeframe and in a manner specified by the study sponsor.

8.3.6 SERIOUS ADVERSE EVENT REPORTING

Any serious adverse events related to the study procedures will be reported to the IRB within 24 hours of knowledge of the event.

All serious adverse events (SAEs) will be followed until satisfactory resolution or until the investigator deems the event to be chronic or the participant is stable. Other supporting documentation of the event may be requested by the study sponsor and should be provided as soon as possible.

Serious adverse events not related to study procedures will be reported to the IRB at the time of continuing review.

8.3.7 REPORTING EVENTS TO PARTICIPANTS

N/A as this is not a treatment study.

8.4 UNANTICIPATED PROBLEMS

8.4.1 DEFINITION OF UNANTICIPATED PROBLEMS (UP)

The Office for Human Research Protections (OHRP) considers unanticipated problems involving risks to participants or others to include, in general, any incident, experience, or outcome that meets all of the following criteria:

- Unexpected in terms of nature, severity, or frequency given (a) the research procedures that are described in the protocol-related documents, such as the Institutional Review Board (IRB)-approved research protocol and informed consent document; and (b) the characteristics of the participant population being studied;

- Related or possibly related to participation in the research (“possibly related” means there is a reasonable possibility that the incident, experience, or outcome may have been caused by the procedures involved in the research); and
- Suggests that the research places participants or others at a greater risk of harm (including physical, psychological, economic, or social harm) than was previously known or recognized.

8.4.2 UNANTICIPATED PROBLEM REPORTING

The investigator will report unanticipated problems (UPs) to the reviewing Institutional Review Board (IRB) and to the principal investigator (PI). The UP report will include the following information:

- Protocol identifying information: protocol title and number, PI’s name, and the IRB project number;
- A detailed description of the event, incident, experience, or outcome;
- An explanation of the basis for determining that the event, incident, experience, or outcome represents an UP;
- A description of any changes to the protocol or other corrective actions that have been taken or are proposed in response to the UP.

To satisfy the requirement for prompt reporting, UPs will be reported using the following timeline:

- UPs that are serious adverse events (SAEs) related to the intervention will be reported to the IRB immediately (within 24 hours) upon the investigator becoming aware of the event.
- Any other UP will be reported to the PI within 7 days of the investigator becoming aware of the problem and to the IRB.
- All UPs should be reported to appropriate institutional officials (as required by an institution’s written reporting procedures), the supporting agency head (or designee), and the Office for Human Research Protections (OHRP) within 1 week of the IRB’s receipt of the report of the problem from the investigator.

8.4.3 REPORTING UNANTICIPATED PROBLEMS TO PARTICIPANTS

Study team will not be reporting unanticipated problems to participants.

8.5 CRISIS PROTOCOL/SAFETY

Crisis procedures: see Appendix A for instructions/crisis procedures document which pertains to the outcome assessments and other interactions with the subjects. The clinic component of the crisis procedures document is provided to clinical study team members as an additional resource for potential management of symptoms identified in clinic as part of the clinical care depression screening procedure.

If there is a need for immediate treatment (e.g., active suicidal ideation, active psychotic symptoms, disorientation, active substance abuse) at any point in time, staff will notify the PI. In both cases, the participant may be referred for psychiatric care. [name], study psychiatrist, will be available for input/guidance if needed. As an additional safety precaution, we will ask each participant upon study enrollment to identify 2 persons whom we can contact in case of an emergency and provide 2 telephone numbers for each of these 2 individuals; if possible. All participants will receive information about safety precautions and procedures to follow in the event that a participant becomes imminently

suicidal. Each participant will be given telephone numbers for the Wake Forest Baptist Health psychiatrist-on-call and crisis hotline. Participants will be able to reach study staff or the psychiatrist-on-call 24-hours a day. If it is determined that a participant is not at risk of imminent harm, we may refer them for additional psychiatric care. If a participant continues to report active suicidal ideation and is at imminent risk, we will ask if there is anyone at home with the participant, speak with that person, and have that person take the participant to the nearest emergency room for an immediate evaluation. If there is no one with the participant, study staff will contact the person's emergency contacts and instruct them to take the participant to the nearest emergency room for an immediate evaluation. If there is no one available to do this, mobile crisis management teams will be contacted and local law enforcement will be called to transport the participant to an emergency room.

Because this is not a treatment study, because we are excluding individuals with passive suicidal ideation at screening, and given the low rate of active suicidality we identified at baseline during our recent learning health system trial (included screening more than 760 individuals using the NDDI-E instrument), we anticipate that active suicidality will be exceedingly rare. All study staff will receive training on the crisis protocol and will have regular meetings with the team to discuss clinical issues.

Additional safety procedures for EMR outcome assessments

If in the EMR outcome assessment arm, a high score on the passive suicidality question of the NDDI-E will trigger an alert with high priority to study staff inbox and/or study team pager indicating that a high score was received.

The study team will call the participant as soon as feasible upon receiving the notification to assess for active suicidality and respond with further action as appropriate.

Staff will be instructed to follow the crisis protocol outlined in Appendix A and complete the Crisis Protocol Event Form. In both cases, the participant may be referred for psychiatric care by a physician or provider: their primary care physician, neurologist, APP, or emergency department physician.

Symptom Worsening

If there is significant symptom worsening at 3 month follow-up compared to baseline or at 6 month follow up compared to the prior assessment, a treatment resource handout will be mailed to the participant (see Appendix B). We will define treatment worsening as worsening in GAD-7 or NDDI-E score by 1 standard deviation^{12;32}.

Specifically, symptom worsening would be defined as the following:

- GAD-7 score increase of 5 points or more
- NDDI-E score increase of 4 points or more

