8.2 SAFETY AND OTHER ASSESSMENTS

Screening Assessments for Safety: in EMR/routine clinic visit

-NDDI-E validated passive suicidality question for safety³⁹: if score indicates potential risk of suicidality, the electronic record system will be triggered to alert the treating epilepsy provider to assess for possible suicidality. These individuals will be excluded from study participation.

Other Enrollment Assessments:

- demographics, medications, medical history (largely based on EMR review)
- brief past psychiatric treatment history interview

Outcome Assessments

3-month assessment

- NDDI-E (validated passive suicidality question for safety)

6-month assessment

- NDDI-E (validated passive suicidality question for safety)

Safety plan at outcome assessments:

-further assess for active suicidality if score on suicidal ideation question of NDDI-E is 3 or higher (using crisis procedures questions outlined in manual and Appendix A). This will be done immediately during telephone outcome assessments.

If an EMR outcome assessment results in a high-risk score on the NDDI-E, high priority alerts (red flag inbasket message or page to study pager) will be sent to study staff, and study staff will then call the participant at the first opportunity available, to assess need for any further action. All efforts will be made to send the EMR outcome assessment questionnaires at the start of a business day to allow maximal opportunity for rapid responses to occur during hours when study staff are available.

Participant emergency contacts may be called if the study staff is unable to reach the participant on the day that a high-risk score was identified. The proposed response time is faster than what may typically occur in standard care practice. For example, new patients to the epilepsy center receive a mailed version of the NDDI-E prior to initial visit, for completion, and these results which may be completed weeks before the visit are only reviewed by clinical staff at the time of the clinic visit.

Further details of safety protocol are outlined in section 8.5 and appendix A.

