9.6 ABBREVIATIONS

9.7 PROTOCOL AMENDMENT HISTORY

The table below is intended to capture changes of IRB-approved versions of the protocol, including a description of the change and rationale. A Summary of Changes table for the current amendment is located in the Protocol Title Page.

Version	Date	Description of Change	Brief Rationale
2	June 3 2019	
 -As the clinical screener instruments can be completed in clinic regardless of mywakehealth enrollment, enrollment step has moved to enrollment stage for any individuals who enroll and do not already have mywakehealth access. -update screening consent text -Add exploratory implementation monitoring to list of study objectives. 	
 -Based upon updated information regarding the screening instruments, we have modified the planned workflow. -better clarity of study info -To support generating preliminary data for potential future studies/dissemination.
3	July 31 2019	
 -remove W-9 language and modify randomization plan to reflect stratification by patient portal enrollment at baseline rather than epilepsy provider, add safety plan for significant symptom worsening at follow up 	
 -W-9 is not needed based on further information gathered by research team -it will be more important to stratify by patient portal enrollment than provider, as this factor is more likely to introduce potential bias if unbalanced for the primary outcome assessment -to provide additional safety measures similar to long-term outcome assessment phase of other mental health studies conducted by study team
4	January 29 2020	
 -added "if possible" to the collection of two emergency contacts with two emergency numbers. (section 8.5) 	Either two emergency contacts or two emergency numbers for each contact was not feasible for all subjects contacted
5	March 3, 2020	
 -removed "BPA" from trigger alert Page 21 	System unable to actually trigger a BPA alert

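### At month 6 the symptom-worsening rule looks back only to the prior assessment, so a stepwise rise of 5–8 GAD-7 or 4–6 NDDI-E points from baseline can go unflagged (minor)

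*Combined protocol and SAP*

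**What the plan says.** Under Symptom Worsening, Section 8.5 sets out when "a treatment resource handout will be mailed to the participant": if there is significant worsening "at 3 month follow-up compared to baseline or at 6 month follow up compared to the prior assessment". The size that counts is described as "worsening in GAD-7 or NDDI-E score by 1 standard deviation", and is then given in points: "GAD-7 score increase of 5 points or more" or "NDDI-E score increase of 4 points or more". Either scale is enough.

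The rule entered with version 3. Section 9.7 records that change as "add safety plan for significant symptom worsening at follow up" and gives additional safety as the reason.

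Two other safeguards run independently of it. Section 8.2 requires staff to "further assess for active suicidality if score on suicidal ideation question of NDDI-E is 3 or higher" at both outcome assessments. Section 8.5 also states: "Participants will be able to reach study staff or the psychiatrist-on-call 24-hours a day".

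**The concern.** The rule names a different comparator at each visit. Month 3 is set against baseline. Month 6 is set against whatever assessment came before it, which is month 3 for anyone who completed it. No other section adds a month-6 versus baseline check for this trigger.

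A participant who deteriorates steadily can therefore finish the study worse than baseline by an amount the protocol regards as significant, without being sent the handout. Month 6 is the last scheduled assessment (Section 1.3), so no later study contact would pick this up. The suicidality item does not fill the gap: it does not respond to a rise in GAD-7, or to a rise in NDDI-E total when item 4 stays below 3.

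**Working it through.** **Inputs (Section 8.5).** Threshold T = 5 for GAD-7 and T = 4 for NDDI-E. The plan presents these as 1 SD, but the SDs are not in the documents, so that derivation cannot be reproduced and the thresholds are taken as written.

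**Condition for a missed case.** Let d1 = month 3 minus baseline and d2 = month 6 minus month 3, both whole numbers. A rise is missed on a scale when d1 < T, d2 < T and d1 + d2 ≥ T.

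**GAD-7.** The largest step that does not trigger is 4.

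| Total rise | Step pairs (d1 + d2) | Count |
|---|---|---|
| 5 | 1+4, 2+3, 3+2, 4+1 | 4 |
| 6 | 2+4, 3+3, 4+2 | 3 |
| 7 | 3+4, 4+3 | 2 |
| 8 | 4+4 | 1 |

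That makes 4 + 3 + 2 + 1 = 10 pairs. The maximum missed rise is 4 + 4 = 8, so a rise of 9 or more must contain a step of at least 5 and is flagged. Relative to the threshold, missed rises run from 5/5 = 1.0 to 8/5 = 1.6.

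**NDDI-E.** The largest step that does not trigger is 3.

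| Total rise | Step pairs (d1 + d2) | Count |
|---|---|---|
| 4 | 1+3, 2+2, 3+1 | 3 |
| 5 | 2+3, 3+2 | 2 |
| 6 | 3+3 | 1 |

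That makes 3 + 2 + 1 = 6 pairs. The maximum missed rise is 3 + 3 = 6, so a rise of 7 or more is always flagged. Missed rises run from 4/4 = 1.0 to 6/4 = 1.5 times the threshold.

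The pair counts describe the shape of the gap. They are not probabilities.

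**Worked paths.** These start from scores that Section 5.1 admits and assume the other scale does not trigger.

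- GAD-7 8 → 12 → 16: steps +4 and +4, 8 points above baseline, no handout. On the bands in Section 2.2, this participant goes from borderline (7–9) to high (10 or more).
- NDDI-E 14 → 17 → 20: steps +3 and +3, 6 points above baseline, no handout. This one goes from borderline (14–15) to high (above 15).
- GAD-7 16 → 8 → 13: steps −8 and +5, 3 points below baseline, handout mailed.

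The documents do not state the scale maxima. I assume 21 for GAD-7 and 24 for NDDI-E, so that 16 and 20 are attainable.

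**If month 3 was missed.** The prior assessment is then presumably baseline, and a rise of T or more is flagged. Two participants with the same baseline and month-6 scores can thus be treated differently because only one of them completed month 3.

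**With a baseline check added at month 6.** Triggering when d2 ≥ T or d1 + d2 ≥ T leaves no path with a month-6 rise of T or more unflagged on either scale.

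**The case against.** The strongest reply is that this is a chosen comparator, not an oversight. One sentence names both reference points. A visit-to-visit rule picks up new deterioration since the last contact and avoids mailing the same person twice for the same rise. On that reading a participant who climbs slowly does not meet the month-6 rule at all, and the protocol is not failing its own definition. It is fair that the definition pairs each threshold with a comparator, and that the month-6 baseline comparison is an addition. But the documents give no rationale for leaving it out, and the purpose recorded in Section 9.7 is worsening at follow-up, not only worsening since the last contact.

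The second reply is that very little is lost, and this largely stands. The study is minimal risk, every participant is given crisis numbers whatever their scores, and the suicidality item works on its own score. A missed case needs month 3 completed, two consecutive sub-threshold rises that add up past the threshold, and no trigger on the other scale. Because participants are enrolled on raised scores, regression to the mean works against such a pattern. These points limit the importance of the gap but do not close it.

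Third, Appendices A and B and the manual are not in the supplied text, so the handout's content and its value to a participant cannot be judged here.

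**Conclusion.** The concern holds and is minor. As written, the rule can leave a participant up to 8 GAD-7 points or 6 NDDI-E points above baseline at month 6 without the handout that the version 3 change was meant to provide. This rests on three conditions: the thresholds are as stated, month 3 was completed so that it is the prior assessment, and neither scale reaches its threshold at either step. How many of the 30 participants would be affected is unknown. The consequence is confined to the mailing; no analysis or decision rule depends on it.

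**What to change.** In Section 8.5, have the handout mailed at month 6 when either score meets its existing threshold against baseline or against the prior assessment. This keeps the recent-worsening check and needs no new data. Baseline-to-month-6 change in both scales is already a planned outcome (Sections 3 and 9.4.3).

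The cost is one clause and one subtraction per scale. There would be some additional mailings, at most one per participant at month 6. These include second copies to people already mailed at month 3, some of whom will have improved since: a GAD-7 path of +10 then −4 ends at +6 from baseline and would be flagged. If that is unwanted, the clause could exclude anyone already mailed at month 3 who has not risen by a threshold amount since.

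Because any added handout follows collection of the month-6 scores, it cannot alter retention or the usual-care change estimates.
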